## **1. Introduction**

### **1.1. Abstract**

The Prophylactic Negative Pressure Wound Therapy in Obese Women at Cesarean Trial is a large pragmatic multi-center randomized clinical trial designed to evaluate the effectiveness, safety and cost-effectiveness of prophylactic negative pressure wound therapy (NPWT) – a closed, sealed system that applies negative pressure to the wound surface via a single-use, battery-powered, portable device – to decrease surgical site infections (SSIs) in obese women. Experimental evidence suggests that NPWT promotes wound healing by removing exudate, approximating the wound edges, and reducing bacterial contamination. Obesity (body mass index [BMI]  $\geq 30\text{kg/m}^2$ ) increases the risk for both cesarean delivery and SSIs compared to non-obese women. The increased risk of SSIs is in part due to the increased thickness of the subcutaneous space, allowing collection of exudates and increasing tension on wound edges, promoting the growth of bacteria, and leading to wound infection and breakdown. Thus, prophylactic NPWT may be particularly effective in this patient population. During the 5-year project period, collaborating perinatal centers will randomize 2850 obese women undergoing cesarean delivery to receive either prophylactic negative pressure wound therapy with the Prevena™ device or standard wound dressing. Women will be followed up to 30 days postoperatively to ascertain study outcomes. The primary outcome for the trial is superficial or deep SSI after cesarean according to the CDC National Healthcare Safety Network definitions. We will also assess other wound complications, adverse events potentially attributable to NPWT and incremental cost per case of SSI prevented and per quality-adjusted life year (QALY).

## 1.2. Specific Aims

**Primary Aim:** Determine the effectiveness of prophylactic NPWT in reducing the rate of SSIs after cesarean in obese women. *We hypothesize that obese women will have lower rates of SSIs after cesarean with use of prophylactic NPWT than with standard care.*

**Secondary Aim#1:** Assess the safety of prophylactic NPWT in obese women as measured by frequency of adverse events including skin blisters, allergic skin reactions, and wound bleeding. *We hypothesize that the rate of adverse events will not be significantly higher with use of prophylactic NPWT than with standard care.*

**Secondary Aim#2:** Evaluate the cost-effectiveness of prophylactic NPWT compared with standard wound dressing in obese women as measured by the incremental cost per case of SSI prevented and per quality-adjusted life year (QALY). *We hypothesize that prophylactic NPWT in obese women at cesarean will be cost-effective.*

## 1.3. Purpose of the Protocol

This protocol describes the background, design, and organization of the trial and represents a written agreement between study investigators. It will be reviewed and approved by the Data Safety and Monitoring Board (DSMB) and the Institutional Review Boards (IRBs) of each center prior to onset of recruitment. A **Manual of Operations** and **Data Collections Forms** will supplement this protocol with further details of study procedures.

## **2. Background**

### **2.1. Introduction**

SSIs are now the most common group of healthcare associated infections (HAIs) and are a significant cause of preventable morbidity and mortality in the United States. These infections result in significant patient suffering and excess health care costs up to \$10 billion each year. For these reasons, prevention of HAIs is a top priority for the US Department of Health and Human Services and the Institute of Medicine. Although several initiatives target HAIs, few are directed at SSIs after cesarean despite the fact that cesarean is the most common major surgical procedure performed in women. In 2013, 1.3 million cesareans were performed in the US and up to 12% of these were complicated by SSIs. Puerperal infection is the 4th most common direct cause of maternal mortality in the US and one of the most common causes of morbidity. Additionally, puerperal infection is an indirect or aggravating factor in many maternal deaths attributed to other causes. Moreover, cesarean delivery is the most important risk factor for puerperal infection.

Obesity (BMI $\geq$ 30 kg/m $^2$ ) further aggravates the problem of SSIs after cesarean: obese women are both more likely than non-obese women to deliver by cesarean and are also at higher risk of SSIs. Obesity complicates over 33% of pregnancies and morbid obesity (BMI  $\geq$  40 kg/m $^2$ ) complicates as many as 10% of pregnancies in the US. The trends of both increasing prevalence of obesity as well as increasing incidence of cesarean suggest that the burden of post Cesarean infections will continue to increase in the US.

#### **2.1.1. Pathophysiology of SSIs after Cesarean in Obese Women**

The mechanism for increased SSI risk in obese women is likely multifactorial. First, an excess of adipose tissue may result in dysregulation of the immune system, impairing chemotaxis and altering macrophage differentiation. Obese women may also have diabetes and other metabolic derangements that further impair the immune system and thus the inflammatory phase of the wound healing process. Second, obesity decreases adipose tissue blood flow and alters collagen structure

and function, limiting infiltration of the space by chemokines, macrophages and growth factors necessary for the first and second stages of wound healing. Obesity also impairs the penetration of preoperative antibiotics, resulting in tissue antibiotic levels below the minimal inhibitory concentration for pathogenic bacteria. Third, the potential subcutaneous dead space allows accumulation of serous fluid and hematomas that serve as a nidus for infection. Physiologic changes of pregnancy and intravenous fluids given during the puerperium exacerbate the accumulation of serous fluid in the subcutaneous dead space after cesarean. Fourth, the thickened subcutaneous tissue places additional mechanical stress on the wound, increasing both superficial stress and lateral tension. The additional shear stress reduces the apposition of cells in the incision, creating additional potential space and increasing the risk of wound dehiscence and infection. Finally, the overhanging pannus in obese women, especially over the site of Pfannenstiel incisions, creates a micro-environment conducive to bacterial proliferation.

### **2.1.2. Prophylactic Negative Pressure Wound Therapy**

Negative pressure wound therapy (NPWT) is a closed, sealed system that applies negative (or sub-atmospheric) pressure to the wound surface. Used since the 1990s to treat open wounds, experimental evidence suggests that NPWT promotes wound healing by removing exudates, approximating the wound edges, and reducing bacterial contamination. Two brands of a modified, single-use, battery-powered, portable NPWT devices PrevenaTM (KCI USA, San Antonio, TX) and PICOTM (Smith & Nephew, Hull, UK) were recently FDA-cleared for prophylactic application after wound closure at the time of surgery. Although the precise mechanism of action of prophylactic NPWT is unclear, experimental evidence suggests that NPWT reduces bacterial contamination, edema, and exudates while increasing microvascular blood flow and promoting granulation tissue by inducing mechanical stress that promotes cell growth. Computer and physical models of NPWT applied to closed incisions demonstrate a decrease in lateral tensile stress by 50% and in shear stress by more than 75%, leading to improved apposition of wound edges. Given the proposed mechanisms of

increased SSI in obese women and the potential mechanism of action of prophylactic NPWT, we hypothesize that prophylactic NPWT will be particularly effective in this population.

### **2.1.3. Existing Data on Prophylactic NPWT**

#### *Non-Obstetric Patients*

Prior studies of NPWT have largely been limited to cohort studies and small randomized trials. Whereas many demonstrated benefit in reducing SSIs and other wound complications, many studies were limited by small samples sizes and confounding by indication. A 2014 Cochrane review of seven randomized trials compared prophylactic NPWT to standard dressing among patients undergoing orthopedic and general surgical procedures. Data from only three of the trials could be combined in a meta-analysis, which showed no significant differences in the rate of SSI. However, a fourth trial, in which data were analyzed by wound rather than by subject, showed a statistically significant 50% reduction in SSI in the NPWT group (14/144 (9.7%) versus 23/122 (18.9%), relative risk 0.52, 95% confidence interval 0.28-0.96). The authors concluded that “there is an urgent need for suitably powered, high-quality trials to evaluate the effects of the newer NPWT products that are designed for use on clean, closed surgical incisions.” No studies of prophylactic NPWT after cesarean were included in this review.

#### *Obstetric Patients*

We identified three retrospective cohort studies and one pilot randomized trial in a systematic review of studies on prophylactic NPWT in obese women after cesarean: (**Table 1**). Two of the retrospective cohort studies compared obese women who received prophylactic NPWT after cesarean to historical controls who received standard dressing. Both studies demonstrated a dramatic reduction in SSIs, reporting no SSIs in the intervention group but 10.4% and 12.0% in the standard dressing controls. The third retrospective study included women who had labored prior to cesarean with at least one additional risk factor for SSI (obesity, preeclampsia, and chorioamnionitis). In this study

prophylactic NPWT was associated with a statistically significant reduction in the risk of wound infection (2.7% versus 11.5%; RR 0.24, 95% 0.07, 0.77; P=0.006) and endometritis (0.9% vs 6.7%, p=0.023).

**Table 1:** Published studies on use of prophylactic NPWT at cesarean in obese women

Study	Design	Device	Inclusion	Surgical site infections, n/N (%)		Relative Risk (95%CI)	Limitations
				NPWT	Control		
Mark et al.,2013	Retrospective cohort	Prevena	BMI>45	0/21 (0%)	5/48 (10.4%)	0.20 (0.01, 3.50)	Small sample size, possible selection bias and confounding by indication
Bullough et al.,2014	Retrospective cohort	PICO	BMI>35	0/50 (0%)	6/50 (12%)	0.08 (0.00, 1.33)	Small sample size, possible selection bias and confounding by indication
Swift et al.,2015	Retrospective cohort study	Prevena	BMI>30 or other risk factors	3/110 (2.7%)	24/209 (11.5%)	0.24 (0.07, 0.77)	Non-randomized design, possible confounding, modest sample size
Chaboyer et al.,2015	Pilot Randomized Controlled Trial	PICO	BMI>30	10/44 (22.7%)	12/43 (27.9%)	0.81 (0.39, 1.68)	Small sample size, included only elective cesareans, possible confounding

[figure not shown]
*Chaboyer et al* recently published a pilot randomized trial in which 87 obese women undergoing elective cesarean were randomized to prophylactic NPWT or standard dressing. Use of prophylactic NPWT was associated with a statistically non-significant 19% decrease in SSI (22.7% vs 27.9%; RR 0.81, 95% CI 0.38-1.68). The authors also found no differences in the frequencies of adverse events (7/44 [15.9%] with NPWT vs 7/43 [16.3%] with standard dressing), and all were minor (skin blisters, erythema, bruising, and wound bleeding). Although more methodologically sound than the others, this

study was limited by including only elective cesareans, the small sample size and differences in prognostic baseline characteristics between the two groups.

Taken together, these studies suggest a 65% decrease in SSIs after cesarean with prophylactic NPWT (random effects model: pooled RR 0.35, 95% CI 0.12-1.04). Although results of these studies are promising, the small sample sizes, between-study heterogeneity, and methodological limitations preclude definitive conclusions on the effectiveness of prophylactic NPWT in obese women after cesarean.

#### *Preliminary Study#1*

We conducted a retrospective cohort study at one of the proposed study sites (University of Alabama at Birmingham) where some physicians use the NPWT in select morbidly obese women undergoing cesarean. The charts of all women with a BMI  $\geq 40$  kg/m^2 undergoing cesarean since NPWT became available were reviewed. Of 762 subjects, 15

**Figure 1: Effect of NPWT on SSIs after Cesarean**

received NPWT. Women who received NPWT weighed more (BMI 68.8 versus 50.0,  $P<0.01$ ) and were more likely to have medical co-morbidities than those who did not receive NPWT. The risk of SSI was remarkably lower with prophylactic NPWT (0% [0/15] versus 11.9% [89/747],  $P=0.16$ ) (Fig.1). Although the study is limited by the non-randomized design, small sample size, and selection bias, the results suggest that prophylactic NPWT may be effective in reducing SSIs after cesarean in obese women.

#### *Preliminary Study#2*

We conducted a pilot RCT (planned N=120) at Washington University Medical Center aimed at: i) assessing the willingness of obese patients to participate in an RCT of prophylactic NPWT after

cesarean, and ii) testing the logistics needed for the trial. We obtained IRB approval for the trial and developed a study protocol. Obese women in labor completed a survey and 67% stated willingness to participate in the study. We consented and randomized 120 obese patients undergoing cesarean in 6 months.

## **2.2. Adverse Effects of Prophylactic NPWT**

The Single Use Prophylactic Negative Pressure Wound Therapy System received FDA marketing approval in 2012. As of September 2015, we identified two reports on the FDA website of blistering at the site of application from the PICO device. A third report of a minor burn from the PICO pump device occurred in a patient after neurosurgery while still unconscious. The patient was found to have been lying on the pump device for a prolonged period of time.

A high rate of skin blisters was reported when NPWT was used after orthopedic surgery, but not with other surgical procedures. This was attributed to use of the adhesive dressing in the setting of marked swelling and edema. Case series suggest approximately 10-15% rate of skin irritation and blisters at the device application site. The majority (~90%) did not require treatment beyond removal of the device. Moreover, adverse events noted with NPWT after cesarean were minor and comparable in frequency to standard dressing.

## **2.3. Cost-benefit of Prophylactic NPWT**

The current FDA-cleared prophylactic single-use NPWT devices cost between \$200 (PICO™) and \$500 (Prevena™) per unit and are increasingly being used after cesarean. Given the cost, prophylactic NPWT must be shown in an independent, suitably powered, high-quality trial to improve clinical outcomes to justify widespread use. However, if proven to be effective at reducing SSIs after cesarean, use of the device may not only be cost-effective, but cost-saving. Two cost-effectiveness analyses of prophylactic NPWT have recently been published suggesting that use prophylactic NPWT after cesarean may be cost effective under a range of conditions. However, because data on its

effectiveness at cesarean are lacking, the cost-effectiveness analyses were based on data extrapolated from other surgical procedures. In addition to the effectiveness data this trial will produce, the accompanying cost-effectiveness analysis will aid decision-making on general clinical use.

## **2.4. Rationale for the Trial**

Infection is one of the top five causes of pregnancy-related death and morbidity in the US and around the world. As rates of cesarean - the strongest risk factor for puerperal infection - continue to rise, the burden of infection is anticipated to increase. Obese women are at particularly high risk of infection after cesarean. Despite the dramatically increased risk of SSI in obese women, no specific intervention exists in this population. Preliminary data from published retrospective cohorts and small randomized trials, as well as our pilot data suggest that prophylactic NPWT may decrease SSI in obese women undergoing cesarean. Therefore, given 1) the persistent high risk of infection and attendant individual and public health costs among obese women undergoing cesarean, 2) the increasing trend in both cesarean and obesity, 3) preliminary data suggesting the effectiveness of NPWT for preventing SSI, and 4) increasing use of NPWT devices with healthcare cost implications, a multicenter trial evaluating the effectiveness, safety and cost-effectiveness of prophylactic NPWT after cesarean in obese women is important and timely.

### **3. Study Design**

#### **3.1. Research Questions**

##### Primary Question

**Compared to standard wound dressing, does the use of prophylactic NPWT reduce the risk of surgical site infection after cesarean in obese women?**

Hypothesis: Compared to standard wound dressing, prophylactic NPWT reduces the incidence of post-cesarean surgical site infection in obese women.

##### Secondary Question 1

**Is the use of prophylactic NPWT associated with increased adverse events such as skin blisters, allergic reaction, wound bleeding?**

Hypothesis: Compared to standard wound care, prophylactic NPWT will not be associated with a significantly higher incidence of adverse events.

##### Secondary Question 2

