## **6. Data Analysis**

### **6.1. Sample Size and Power**

#### **6.1.1. Primary Aim – Effectiveness**

The total sample size for the trial is estimated based on the primary outcome. We then estimate, on the basis of the sample size for the primary aim, the power we will have to detect clinically significant differences in the secondary aims. All sample size and power estimates are based on two-tailed tests, enabling us to detect an increase or decrease in rates of outcomes with use of prophylactic NPWT.

The baseline rate of SSIs in obese women from our preliminary data is 11.6%. Furthermore, rates of SSIs at the study sites in all women range from 6 to 12% and are expected to be higher in obese women. Assuming a conservative baseline rate of 10%, we estimate that a total of **2850** subjects (1425 NPWT and 1425 standard care) will be sufficient to detect a 30% relative difference in SSIs, with 80% power and 5% significance level and

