#### **6.1.2. Secondary Aim 1 - Safety**

The sample size of 2,850 subjects for the primary aim will be sufficient to detect at least a 25% difference in composite adverse events between the two groups with 85% power and significance

level of 5%. This represents the difference between a 16% rate of composite adverse events with NPWT (based on preliminary data) and 12% with standard dressing.

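### The safety hypothesis of Secondary Aim 1 can be upheld by a non-significant difference test while the interval still includes the 4-point increase the plan is powered to detect; no limit is set for reading the interval

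*Combined protocol and SAP*

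**What the plan says.** Section 1.2 states the hypothesis of Secondary Aim 1 as "the rate of adverse events will not be significantly higher with use of prophylactic NPWT than with standard care". Section 3.1, under Secondary Question 1, repeats it: "prophylactic NPWT will not be associated with a significantly higher incidence of adverse events".

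Section 6.1.1 says that "All sample size and power estimates are based on two-tailed tests", and that the fixed sample size is used to work out "the power we will have to detect clinically significant differences in the secondary aims". Section 6.1.2 then says the trial can detect "at least a 25% difference in composite adverse events between the two groups with 85% power", and explains: "This represents the difference between a 16% rate of composite adverse events with NPWT", against "12% with standard dressing".

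Section 6.2.1 compares categorical secondary outcomes with the Cochran-Mantel-Haenszel test and plans relative risks with 95% confidence intervals for them. Section 4.8.2 lists three kinds of adverse event among the secondary outcomes but does not define the composite that 6.1.2 powers. Neither document section gives an acceptable increase, a margin, or a rule for reading the interval on adverse events.

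**The concern.** The hypothesis is one of no significant increase, and the only test supplied is a test of no difference. Failing to reject that null hypothesis is not evidence that an important increase is absent. Yet a report that follows the wording of 1.2 and 3.1 would count the hypothesis as supported whenever the test is non-significant.

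At stake is the answer to one of the trial's three stated questions. The trial could report that the device does not raise adverse events when its own confidence interval includes an increase as large as the one it was powered to detect.

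**Working it through.** **Inputs**
- Women per arm: 1425 randomised, 5% loss (6.1.1, Table 4). 1425 × 0.95 = 1353.75, taken as 1354.
- Rates: 16% with NPWT, 12% with standard dressing (6.1.2). The difference is 4 points and the relative risk is 16/12 = 1.33.
- Two-sided 5% test, z = 1.96 (6.1.1, 6.1.2).
- Alternative standard rate: 16%, because the published pilot trial in 2.1.3 had 7/43 = 16.3% on standard dressing.
- Margin: none in the documents. Four points is assumed, with 3 and 5 as a range.

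All figures use the unstratified normal approximation for two proportions.

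**1. The plan's own power.** Power = Φ[(d − 1.96·SE0)/SE1], where SE0 = √(2p̄(1−p̄)/n) and SE1 = √(p₁(1−p₁)/n + p₂(1−p₂)/n).
- n = 1354: SE0 = 0.01334, SE1 = 0.01331. (0.04 − 0.02614)/0.01331 = 1.04, so power is 85.1%.
- n = 1425: SE0 = 0.01300, SE1 = 0.01298. The result is 1.12, so power is 86.8%.

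The stated 85% is reproduced as a two-sided difference test. A one-sided test would give 91% to 92%.

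**2. How often a real increase is non-significant (n = 1354).**

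| True rates, standard → NPWT | SE0 | SE1 | (d − 1.96·SE0)/SE1 | Non-significant |
|---|---|---|---|---|
| 12% → 16% | 0.01334 | 0.01331 | 1.04 | 15% |
| 12% → 15% | 0.01313 | 0.01312 | 0.32 | 37% |
| 12% → 14% | 0.01293 | 0.01292 | −0.41 | 66% |
| 16% → 20% | 0.01477 | 0.01475 | 0.75 | 23% |

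**3. What a non-significant result can leave open (n = 1354, 12% observed on standard dressing).** Upper limit = d + 1.96·SE1.
- d = 1.5 points: z = 0.015/0.01282 = 1.17, p = 0.24. Upper limit = 0.015 + 1.96 × 0.01282 = 4.0 points.
- d = 2.5 points: z = 0.025/0.01303 = 1.92, p = 0.055. Upper limit = 0.025 + 1.96 × 0.01302 = 5.05 points.
- Significance is reached at about 2.55 points, where the upper limit is 5.1.

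With 16% observed on standard dressing, the largest non-significant excess is about 2.9 points, with an upper limit of 5.7.

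**4. Judging by the upper limit instead.** If the arms are equal, P(upper limit < margin) = Φ(margin/SE − 1.96), with SE = √(2p(1−p)/1354).
- Both 12%: SE = 0.01249. 0.04/0.01249 − 1.96 = 1.24, giving 89%.
- Both 16%: SE = 0.01409. 0.04/0.01409 − 1.96 = 0.88, giving 81%.
- A true 4-point increase passes with probability Φ(−1.96) = 2.5%.
- A 3-point margin is met 67% (both 12%) or 57% (both 16%) of the time. A 5-point margin is met 98% or 94%.

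**5. Low event rates.** Take 3% against 5% as an assumed case: SE1 = 0.00752. The 4-point limit is met with probability Φ(0.02/0.00752 − 1.96) = Φ(0.70) = 76%, although the difference is non-significant only 24% of the time. A margin alone would therefore often pass a significant increase. Requiring also that the increase is not significant brings the 76% down to 24%. At 12% the extra condition costs nothing: the margin already needs an observed excess below 0.04 − 1.96 × 0.01249 = 1.6 points, well short of significance.

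**6. Scale.** Four points and a relative risk of 1.33 are not interchangeable limits. At an observed 13.5% against 12%, the log relative risk has SE √(0.88/(0.12 × 1354) + 0.865/(0.135 × 1354)) = 0.1007. The upper limit is then 1.125 × exp(1.96 × 0.1007) = 1.37, while the risk difference has an upper limit of 4.0 points. The scale of the margin must be stated.

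**The case against.** A reader might infer that the plan contains an explicit rule that p > 0.05 means safe. It does not. The disputed sentences are research hypotheses, and the question in 3.1 asks whether adverse events are increased, which a difference test does address. The trial is also powered at 85% to find harm. This stands. The weakness is that the hypothesis as worded invites that reading and nothing else in the plan says when it is supported.

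Section 6.2.1 already plans relative risks with 95% intervals for secondary outcomes, so the material for a sound judgement will be there. This also stands. What is missing is a limit against which to read the interval.

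The 15% is simply the complement of the power that 6.1.2 discloses, and the 37% and 66% concern increases of 3 and 2 points, which the plan does not call clinically significant. That is right, and the point rests on the 4-point figures.

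A reader might also take 4 points as the plan's tolerance for harm. The documents do not support that. Section 6.1.1 does speak of clinically significant differences, but the 4 points come from what a sample size fixed by the primary aim can detect, and 6.1.2 expresses them as a 25% relative difference. A difference worth detecting is not automatically one that may be accepted.

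Finally, it is tempting to say that the present wording rewards under-recording of mild reactions. That argument should not be used, because under-recording eases a margin rule as well. If half the events were missed, so that 12% and 16% were recorded as 6% and 8%, non-significance would occur 47% of the time and the 4-point limit would be met 53% of the time.

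The aim is secondary, section 7.2 classes the reactions as mild or moderate, serious events are reported separately, and the monitoring board reviews adverse events every six months. This limits the weight of the point.

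**Conclusion.** The concern holds as a gap between hypothesis and analysis. The hypothesis is framed as absence of significance, the test is a two-sided difference test, and no limit is given for the planned intervals. With 1354 per arm and 12% on standard dressing, observed excesses of about 1.5 to 2.5 points would uphold the hypothesis as worded while the upper limit lies between about 4.0 and 5.1 points. A true 4-point increase would be non-significant 15% of the time, or 23% at a 16% standard rate.

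These figures assume 5% loss in each arm, rates near 12% to 16%, and no effect of stratification on precision. With all 1425 per arm they change little (13% in place of 15%, 21% in place of 23%). The stated 85% power is correct. The primary conclusion on surgical site infection is unaffected.

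**What to change.** Amend 1.2, 3.1 and 6.2.1:

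- Remove non-significance as the basis for the safety conclusion, and state that p > 0.05 will not be reported as showing that NPWT does not increase adverse events.
- Define the composite as any one of wound bleeding, allergic reaction or skin blistering.
- Report its risk difference (NPWT minus standard) and relative risk, each with a 95% confidence interval.
- Claim no important increase only if the upper 95% limit excludes a pre-stated margin, on a stated scale, and the increase is not itself statistically significant. The second condition guards against low event rates.
- Otherwise report that an important increase has not been excluded.

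The 4-point difference in 6.1.2 (relative risk about 1.33 over 12%) is a candidate margin. The sponsor should confirm and justify it, or choose another, before outcome data are seen by arm. The planned sample supports 4 points at 81% to 89% if the arms are equal, but not 3 points (57% to 67%).

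The cost is wording only, with no new data or patients. The downside is that, at the event rates the plan expects, the safety claim becomes harder to make.
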